6.1 Inclusion Criteria

- 1. Over and including 18 years
- 2. Male and female
- 3. Symptoms of faecal incontinence
- 4. Willing and able to provide written informed consent.

6.2 Exclusion Criteria

- 1. Painful or acute perianal conditions: fissures/perianal abscess/recent trauma
- 2. Anal cancer
- 3. Anorectal surgery in the last 3 months

6.3 Recruitment

Referrals to each trust are triaged by the overseeing consultant. Potential participants for the study will be identified. At ASPH suitable referrals will be tracked to a dedicated pelvic floor clinic for review by the student researcher. Participants who meet the inclusion/exclusion criteria will be offered a patient information sheet and given an appointment in a dedicated anorectal physiology session (ARP). At UCLH suitable referrals will be contacted via telephone by the student researcher, should they wish to enroll they will receive a PIS and given an appointment in a dedicated ARP session. Participants will only be assessed and followed up in their recruiting trust.

Participant recruitment at a site will only commence when the trial has:

- 1. Been confirmed by the Sponsor (or it's delegated representative), and
- 2. Been issued an 'NHS permission letter'.

6.4 Informed consent

It is the responsibility of the Investigator, or a person delegated by the Investigator to obtain written informed consent from each participant prior to participation in the trial, following adequate explanation of the aims, methods, anticipated benefits and potential hazards of the trial.

The student researcher is suitably qualified and experienced in the consent process, and has been delegated this duty by the CI/ PI on the Staff Signature and Delegation of Tasks.

"Adequate time" must be given for consideration by the participant before taking part. Consent will be sought at least 24 hours after being given the study documentation It must be recorded in the medical notes when the participant information sheet (PIS) has been given to the participant.

The Investigator or designee will explain that participants are under no obligation to enter the trial and that they can withdraw at any time during the trial, without having to give a reason.

No trial procedures will be conducted prior to the participant giving consent by signing the Consent form. Consent will not denote enrolment into trial.

A copy of the signed Informed Consent form will be given to the participant. The original signed form will be retained in the trial file at site and a copy placed in the medical notes.

The PIS and consent form will be reviewed and updated if necessary throughout the trial (e.g. where new safety information becomes available) and participants will be re-consented as appropriate.

7. Product/Interventions

The study is investigating the use of the MAPLe device in the assessment of FI. The MAPLe is a medically certified device distributed by Novuqare (Appendix 2). The certification covers the diagnosis and management of faecal and urinary incontinence; it will be used within in its certification.

The MAPLe device consists of a probe that can be used vaginally or anally and an electric receiving device. The probe has 24 surface electrodes that detect the electromyography (EMG) of the different groups of muscles of the pelvic floor. These results are analysed by the receiver to provide numerical values and greyscale depiction of the EMG of each muscle group and location of reduced or increased activity.

For the assessment of faecal incontinence the probe will be placed anally. The participant will be asked to perform a set protocol of maneuvers to identify areas of weakness in the pelvic floor. Participants will undergo assessment with MAPLe at the ARP session.

8. Study procedures

8.1 **Pre-intervention assessments**

The following study specific procedures will be carried out after consent to assess the participant's eligibility:

- □ Medical History recorded
- □ Surgical History recorded
- □ Concomitant Medication recorded

All pre-treatment procedures will be carried out as specified in the schedule of assessments (appendix 1).

8.2 Registration Procedures

Participant registration will be undertaken centrally by the **student researcher** when booking ARP. Eligibility will be confirmed and participants will be allocated an individual study number. At ARP participants will complete a pre-filed consent form.

Participants are considered to be enrolled into the study following: consent, pre-treatment assessments (see section 8.1), confirmation of eligibility, completion of the registration process, allocation of the participant study number by the central coordinating team.

8.3 Intervention procedures

Participants will be asked to attend an ARP session at their recruiting trust **to undertake assessment by the student researcher**. During this session each participant will complete an incontinence questionnaire (appendix 3), quality of life questionnaire(37) (appendix 4), provide a prescribed history (appendix 5) and undergo standardised ARP studies (appendix 6, 7):

Anal ultrasound

- UCLH: performed in the radiology department by trained sonographer.
- □ ASPH: performed during anorectal physiology session by trained study representative

HRAM

□ Performed at anorectal physiology session by trained study representative

MAPLe

□ Performed at anorectal physiology session by trained study representative.

8.4 Subsequent assessments and procedures

The ARP results for each participant will be discussed at their local multi disciplinary team meeting in accordance with current practice. Participants who are offered treatment will be followed up at 6 months in their recruiting trust for repeat assessment with MAPLe. Participants who are offered neuromodulation will receive interval assessment with MAPLe during the placement of the implanted device. Should not follow up be offered participation is complete.

A schedule of all trial assessments and procedures is set-out in Appendix 1.

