Appendix 1 - Schedule of assessments			
Appendix 2 - CE Certificate			
Appendix 3 - St Mark's Incontinence Score			
Appendix 4 - Quality of Life Questionnaire			

Appendix 5 - Protocol for MAPLe	
References	40

List of abbreviations

AE	Adverse Event
CI	Chief Investigator
CRF	Case Report Form
FI	Faecal Incontinence
MAPLe	Multiple Array Probe Leiden
AUS	Anal Ultra Sound
HRAM	High Resolution Anal Manometry
ARP	Anorectal Physiology
EMG	Electromyography
sEMG	Surface Electromyogrphy
GCP	Good Clinical Practice
IB	Investigator's Brochure
ICF	Informed Consent Form
ISF	Investigator Site File
MDT	Multi-Disciplinary Team
NHS R&D	National Health Service Research & Development
PI	Principal Investigator
PIS	Participant Information Sheet
QA	Quality Assurance
QC	Quality Control
REC	Research Ethics Committee
SAE	Serious Adverse Event
SDV	Source Document Verification
SOP	Standard Operating Procedure
TMG	Trial Management Group
TSC	Trial Steering Committee

1. Trial personnel

See protocol cover page for Chief Investigator and Sponsor contact details.

Statistician

[name]

e-mail: [contact]

[contact]

2. Summary

Objectives:	Primary Objective: To determine the role of MAPLe in the assessment of Faecal Incontinence (FI) in defined patient groups. Secondary Objective: Identify which patient groups benefit from physiological testing with MAPLe and receive targeted treatment
Type of trial:	This is a multi-centre cohort study investigating FI
Trial design and methods:	The study will take place across two trusts with specialist pelvic floor services.
	Participants will be recruited via referrals for anorectal physiology (ARP) with symptoms of FI meeting the inclusion/exclusion criteria.
	Participants will complete incontinence and quality of life questionnaires, undergo routine ARP with high resolution manometry (HRAM) and anal ultrasound (AUS), and additional assessment with MAPLe. Each assessment will be performed in accordance with a standardised protocol.
	ARP results will be discussed at the local MDT, should treatment be offered, the participant will undergo further testing with MAPLe, if no treatment if offered participation is complete.
Trial duration per participant:	12 months
Estimated total trial duration:	18 months
Planned trial sites:	Multi-Site: University College London Hospitals (UCLH)
	Ashford and St Peter's NHS Foundation Trust (ASPH)
Total number of participants planned:	120

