3.1 Assessment and Management of Risk

The table below summarise the risks and mitigations of all test above standard care that are being performed in a table:

Intervention	Potential risk	Risk Management
Assessment with MAPLe device	The device will be placed anally and record sEMG, not providing stimulation. As the device will be used in the same nature as current assessment devices no additional risk is perceived.	Performed by trained operator.

4. Objectives

Primary: To determine the role of MAPLe in the assessment of FI in defined patient groups.

Secondary: To determine if targeted treatment is achieved following assessment with MAPLe.

5. Trial design

This is cohort study of participants with symptoms of faecal incontinence. It will take place across two hospital trusts, both able to provide specialist pelvic floor services and facilities required to meet the needs of the study and follow up required by the participants. The use of two sites aims to increase the yield and diversity of participants. The sample size for the study is 120 participants.

Following a stringent selection and recruitment process, participants will be invited to a designated ARP session where they will be consented, complete an incontinence and quality of life questionnaire, and undergo ARP assessment. This will comprise of the current gold standard, AUS and HRAM, and additional assessment with MAPLe using a standardised protocol. Through undertaking all three tests participants will act at their own controls. Participant participation will conclude following ARP assessment unless treatment is deemed necessary by their local MDT. These participants will be followed up at 6 months with interval MAPLe assessment and incontinence and quality of life questionnaire.

The results will undergo statistical analysis to determine non-inferiority of MAPLe in assessing FI. For analysis participants will be allocated to the following groups: fistula/chronic perianal conditions, obstetric injury <12 months, obstetric injury >12months, neurogenic. Each group will be analysed using symptoms profile and MAPLe results to identify correlation. Comparison of MAPle results pre and post treatment will determine if targeted treatment has been achieved.

An expert panel of pelvic floor specialists will be formed to determine the additional benefit of MAPLe in a clinical context. The panel will consist of 3-6 specialists within the field. To reduce bias,

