11.2 Secondary outcome(s)

The secondary outcome is to determine if following assessment with MAPLe targeted treatment is achieved. This will be defined by improvement in physiological assessment with MAPLe and incontinence questionnaires. This will be measured at 6 months following the end of recruitment at the end of study.

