11.5.2 Secondary outcome analysis

To determine if targeted treatment has been achieved participants will be grouped according to the treatment received: biofeedback, neuromodulation, rectal irrigation, and surgery.

Statistical comparison between MAPLe results pre and post treatment for each participant per group will be performed and analysed.

12. Record keeping and archiving

At the end of the trial, all essential documentation will be archived securely by the CI for a minimum of 20 years from the declaration of end of trial.

Essential documents are those which enable both the conduct of the trial and the quality of the data produced to be evaluated and show whether the site complied with all applicable regulatory requirements.

The sponsor will notify sites when trial documentation can be archived. All archived documents must continue to be available for inspection by appropriate authorities upon request.

13. Oversight Committees

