Appendix 1 - Schedule of assessments

	Screening (Pre- treatment assessment)	Intervention phase		Final visit	
Visit No:	1	2	3	4	
	Day – X to Day -X	Day 1	Day 7	6 Months	
Window of flexibility for timing of visits:			+/- 7 Days	+/- 14 days	
Informed Consent		Х			
Medical History	Х				
Physical Examination					
Eligibility confirmation	Х	Х			
Faecal incontinence Questionnaire		Х			
Quality of Life Questionnaire	Х				
Anal Ultrasound	UCLH X	ASPH X			
Prescribed History		Х			
HRAM		Х			
MAPLe		Х		If treatment advised x	
MDT			Х		
Adverse Events review	Х	Х	Х	Х	
Concomitant Medication review (if applicable)	Х	Х			

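### The 6-month MAPLe that serves as the post-treatment value is triggered by an offer of treatment, and nothing counts the 6 months from when treatment starts

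*Combined protocol and SAP*

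**What the plan says.** Three places schedule the follow-up reading.

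- Section 8.4: "Participants who are offered treatment will be followed up at 6 months in their recruiting trust for repeat assessment with MAPLe". The trigger is the offer of treatment, and the 6 months has no stated origin. The section adds: "Participants who are offered neuromodulation will receive interval assessment with MAPLe during the placement of the implanted device".
- Section 5, after describing the local MDT decision: "These participants will be followed up at 6 months with interval MAPLe assessment and incontinence and quality of life questionnaire". Again no origin is given.
- Appendix 1 has the baseline MAPLe on Day 1, the MDT on Day 7 (+/- 7 days) and the final visit at 6 months (+/- 14 days). The final MAPLe is marked "If treatment advised x". There is no column for treatment, no entry for the MAPLe at device placement, and neither questionnaire is marked at the final visit.

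The analysis is in section 11.5.2: "participants will be grouped according to the treatment received: biofeedback, neuromodulation, rectal irrigation, and surgery", followed by "Statistical comparison between MAPLe results pre and post treatment for each participant per group will be performed and analysed". Section 11.2 says of the secondary outcome: "This will be measured at 6 months following the end of recruitment at the end of study".

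**The concern.** The visit is triggered by treatment being offered or advised, while the analysis needs treatment to have been received. No rule links the two. There is no deferral of the visit if treatment has not begun, no time on treatment to be reported, and no later reading.

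Following Appendix 1 as written, the reading is taken at 6 months whether or not treatment has started. A participant who started late could show no improvement on MAPLe because of timing, and section 11.5.2 could not tell this apart from treatment that failed to hit its target. A participant still waiting has no post-treatment value at all. A start date may be recoverable from hospital notes afterwards, but a mistimed reading cannot be retaken.

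Implanted neuromodulation is the most plausible case. The background section calls it second line and describes a temporary-wire test that must succeed before a permanent device is offered.

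**Working it through.** **1. Which origin do the stated durations support?** Inputs: recruitment over 12 months (section 11.4); expected study duration of 18 months from first recruitment, and end of study 6 months after the last participant's last visit (section 8.6); 12 months in the Summary row headed "Trial duration per participant".

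- Visit counted from Day 1: 12 + 6 = 18 months. This reproduces the 18-month figure and agrees with section 11.2.
- 12 months per participant: 12 + 12 = 24 months, which does not agree.
- End of study 6 months after a last visit at month 18: 18 + 6 = 24 months, which does not agree.

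Day 1 is therefore the best-supported origin, but it is inferred.

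**2. Time on treatment if the origin is Day 1.** Let w be the months from Day 1 to treatment start. The documents do not give w, so the values below are assumptions.

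Time on treatment = 6 - w, with a visit window of 14/30.4 = 0.46 months either way.

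| Assumed w (months) | Time on treatment (months) |
|---|---|
| 1 | 5 |
| 3 | 3 |
| 5 | 1 |
| more than 6 | none: reading precedes treatment (window aside) |

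**3. The same check from the MDT, in days.** Six months is 6 x 30.44 = 182.6 days. With the MDT at 7 days, 182.6 - 7 = 176 days remain, and all waiting and treatment must fit inside them. With both windows the range is 182.6 - 14 - 14 = 155 to 182.6 + 14 - 0 = 197 days.

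| Assumed wait after MDT (weeks) | Nominal days on treatment | Range with windows |
|---|---|---|
| 8 | 176 - 56 = 120 | 99 to 141 |
| 12 | 176 - 84 = 92 | 71 to 113 |
| 18 | 176 - 126 = 50 | 29 to 71 |
| 24 | 176 - 168 = 8 | 0 to 29 |

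Nothing is left at 175.6/7 = about 25 weeks (22 to 28 with the windows).

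**4. If the visit is set 6 months after treatment start.** A last participant recruited at month 12 is read at 12 + w + 6, which is month 19, 21 or 23 for w = 1, 3 or 5. Each participant's time in the study is w + 6 months, which stays within 12 months for w up to 6. With a 3-month interval, 12 + w + 3 is at most 18 for w up to 3.

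**The case against.** The harm needs a long wait, and the documents report none. Little or no treatment at the reading takes roughly 18 to 25 weeks or more between MDT and start; shorter waits leave months of exposure. It also needs the Day 1 origin, and the 12 months per participant would leave room for a visit anchored on treatment. Follow-up at a fixed time after assessment is, besides, a coherent choice for an objective about what is achieved following assessment with MAPLe. Because section 11.5.2 groups by treatment received, someone untreated at 6 months would on its wording be missing rather than miscounted. As for neuromodulation, first-line failure may precede enrolment, and the temporary-wire phase is itself stimulation.

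Most of this stands and limits the point. It does not remove it: no section adopts the treatment-anchored reading, and section 11.5.2 does not separate a participant treated for one month from one treated for five. The MAPLe at device placement does not help either, since it is taken as permanent treatment begins and does not move the 6-month visit.

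Three stronger readings are tempting and unsupported. A reader might infer that many follow-up readings will precede treatment; no waiting times are given, so no frequency can be claimed. A reader might calculate a share of participants who could not complete 6 months of treatment by month 18; but section 8.6 calls 18 months an expected duration and ties the end of study to the last visit, so month 18 is not a hard cut-off. A reader might conclude that treatment dates will not be recorded; section 10.4 names none, but its list is not a CRF specification, the CRF is not among the documents, and the notes may hold the dates.

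**Conclusion.** The point holds in a limited form. The reading used as post-treatment is scheduled on an offer or advice of treatment, with no origin tied to treatment start and no rule for late starters. That much is on the face of the text. Its size is conditional: with a Day 1 origin (inferred), exposure is 6 months minus an unstated wait, falling to about zero when treatment starts some 25 weeks after the MDT. Greater exposure to the problem for implanted neuromodulation is a plausible inference, not a finding.

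Only the secondary outcome is affected, and no contrast between treatments is planned. The change is worth making before recruitment because it is cheap and a mistimed reading cannot be recovered. Confidence is medium.

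**What to change.** - State one time origin for the follow-up MAPLe, the same for all treated participants, and bring the durations in sections 2, 8.6 and 11.2 into line with it.
- Record the treatment start date on the CRF. For neuromodulation record both the temporary-wire date and the permanent placement date.
- Add to Appendix 1 the MAPLe at device placement and the follow-up questionnaires that section 5 requires.
- Preferably, set the follow-up MAPLe and questionnaires at one fixed interval after treatment start.
- If Day 1 plus 6 months is kept for calendar reasons, keep it for everyone. In section 11.5.2, count a reading as post-treatment only if treatment had started, report those not yet treated separately, and report time on treatment by treatment group. Do not add a minimum-exposure exclusion: any threshold would be arbitrary and would select participants by how quickly they reached treatment.

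The cost is a few date fields, some schedule entries and a sentence on the origin. The preferred option moves the last reading later by about the wait (month 19, 21 or 23 for waits of 1, 3 or 5 months). A 3-month interval would stay within 18 months for waits up to 3 months, at the price of shorter exposure. The fallback adds no study time but may leave fewer participants with a post-treatment value.

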8.5 Discontinuation/withdrawal of participants

In consenting to participate in the study, participants are consenting to intervention, assessments, follow-up and data collection.

A participant may be withdrawn from trial whenever continued participation is no longer in the participant's best interests, but the medical reasons for doing so will be recorded. Personal reasons will not be recorded. Reasons for discontinuing the trial may include:

- \Box Ineligibility undetected at screening
- \Box Deviation from protocol
- □ Significant non-compliance with study requirements (refusal/difficult examination)
- \Box Withdrawal of consent

The participants will remain in the study for the purpose of data analysis and the reason for withdrawal recorded in the CRF and medical notes. If a participant explicitly states they do not wish to contribute further data to the trial their decision must be respected and recorded in the CRF and medical notes.

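### Section 8.5 keeps participants found to be ineligible in the data analysis, and section 11.5 defines no analysis set that separates them

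*Combined protocol and SAP*

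**What the plan says.** Section 8.5 lists reasons for discontinuing, among them "Ineligibility undetected at screening". The next statement covers everyone on the list: "The participants will remain in the study for the purpose of data analysis". One exception follows: "If a participant explicitly states they do not wish to contribute further data to the trial their decision must be respected".

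Section 11.5 describes Bland-Altman, correlation and regression analyses, the latter two within four cause groups, and a pre/post treatment comparison. It names no analysis population and no sensitivity analysis. Section 5 describes a cohort in which each participant has AUS, HRAM and MAPLe and so serves as their own control.

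On how eligibility is checked:

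- Section 6.2 excludes, among others, "Painful or acute perianal conditions: fissures/perianal abscess/recent trauma".
- Section 8.1 says "The following study specific procedures will be carried out after consent to assess the participant's eligibility" and lists medical history, surgical history and concomitant medication.
- Section 8.2 has eligibility confirmed when the physiology session is booked, with the consent form completed at the session.
- Section 6.3 has referrals triaged by a consultant. ASPH then reviews patients in clinic, while "At UCLH suitable referrals will be contacted via telephone by the student researcher".
- Appendix 1 marks eligibility confirmation at visits 1 and 2. In the text supplied, its row "Physical Examination" has no visit marked.

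**The concern.** Sections 6.1 and 6.2 define the people to whom the results are meant to apply. Keeping everyone who entered is usually defended as protecting a randomised comparison. Nothing is randomised here, so that defence is not available.

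If someone outside the criteria completes MAPLe with HRAM or AUS, the plan as written has no rule that keeps the pair out of the primary analyses. Agreement, correlation and the proportion of abnormalities correctly identified would then describe a mixture of the defined population and people the protocol meant to leave out. Acute perianal disease is an exclusion, while fistula and chronic perianal conditions form one of the four analysis groups, so the boundary matters to at least one group's results. The groups are small enough for one or two participants to be visible in the estimates.

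**Working it through.** **1. The rule.** Three provisions, read together:

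| Provision | Effect on a participant found ineligible late |
|---|---|
| 8.5, list of reasons | May be discontinued |
| 8.5, next sentence | Remains for data analysis |
| 8.5, exception | Applies only if the participant refuses further data |
| 11.5 | No analysis set or sensitivity analysis to remove or isolate the case |

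Nothing in section 11 overrides the sentence in 8.5.

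**2. The plan's own figure.** Section 11.3 sets 30 per group in 4 groups: 30 × 4 = 120, which reproduces. No significance level, power, effect size or margin is given. What follows is illustration under stated assumptions.

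**3. Weight on a proportion.** One case in a group of 30 carries 1/30 = 3.3 percentage points.

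**4. Effect on a correlation.** Take 30 − k eligible participants, standardised on both measures with correlation r₀, and add k cases, each v SD from the mean on both.

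- Sxx = Syy = (30 − k − 1) + kv² − (kv)²/30
- Sxy = (30 − k − 1)r₀ + kv² − (kv)²/30 if the cases are concordant. The sign of the added part reverses if they are discordant.
- r = Sxy/Sxx

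With r₀ = 0 and concordant cases:

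| k | v | Sxy | Sxx | r |
|---|---|---|---|---|
| 1 | 3 | 9 − 0.3 = 8.7 | 28 + 8.7 = 36.7 | 0.24 |
| 2 | 2 | 8 − 0.533 = 7.467 | 27 + 7.467 = 34.467 | 0.22 |
| 2 | 2.5 | 12.5 − 0.833 = 11.667 | 27 + 11.667 = 38.667 | 0.30 |
| 2 | 3 | 18 − 1.2 = 16.8 | 27 + 16.8 = 43.8 | 0.38 |

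At n = 30 and an assumed two-sided 5% level, the critical value is 0.361. Only the last row crosses it. If the same cases are discordant, each r changes sign.

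With r₀ = 0.5 (assumed), one case at 3 SD gives (14 + 8.7)/36.7 = 0.62 if concordant and (14 − 8.7)/36.7 = 0.14 if discordant. The direction is therefore not determined.

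**5. How often.** The documents give no rate of late-found ineligibility. For an assumed rate p, the expected number is 120p and the chance of at least one case in a group of 30 is 1 − (1 − p)³⁰.

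| Assumed p | Expected in 120 | At least one in a group of 30 |
|---|---|---|
| 2% | 2.4 | 45% |
| 5% | 6 | 79% |
| 10% | 12 | 96% |

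These count ineligible participants. Those with completed paired tests would be the same number or fewer.

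**6. Price of exclusion.** With r = 0.5 (assumed), the 95% interval is tanh(atanh 0.5 ± 1.96/√(n − 3)). It runs from 0.17 to 0.73 at n = 30 and from 0.15 to 0.74 at n = 27, which is a group after 10% are removed. The loss of precision is small.

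**The case against.** The strongest reply is that the sentence in 8.5 is ordinary retention of data already collected, since the opt-out for further data follows at once. On that reading the plan has simply not defined its analysis set. That is a fair account of the cause. It does not remove the gap: the sentence follows directly on a list that includes late-found ineligibility, and nothing later limits it.

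A reader might also infer that eligibility rests on history and medication alone, so that perianal exclusions will probably be missed until a probe is placed. The documents do not support that. There is consultant triage, clinic review at ASPH, confirmation at registration as a condition of enrolment, and a second confirmation on Day 1. At UCLH, the site that recruits by telephone, Appendix 1 puts the ultrasound at visit 1, before HRAM and MAPLe. Recent surgery, known cancer and painful conditions should largely emerge from a history. A test abandoned at the probe yields no MAPLe value to pair. The blank examination row may be an unused template line or an effect of text extraction. What stands is narrower: none of these steps is described as a check of the perianal exclusions, and 8.5 itself anticipates that ineligibility can go undetected.

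A third inference would be that retained cases inflate the association between MAPLe and the other tests. The calculation shows this only for concordant extreme cases. It passes the critical value only with two cases at 3 SD in one group, and no document supports that pattern.

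**Conclusion.** The point holds as a gap in the analysis rules. The plan says that participants found ineligible stay in the data analysis, and it provides neither an eligible-only main analysis nor a sensitivity analysis. Such people can enter the primary analyses if their paired tests were completed.

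The number of cases and the direction of any bias are unknown. The one firm figure is the weight of 3.3 percentage points per case in a planned group of 30. The correlation results depend on assumed distances from the mean and assumed concordance, and they show sensitivity in either direction, not a predicted bias. This is worth correcting before analysis, but it does not show that the study's results will be wrong.

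**What to change.** **Analysis population (8.5 and 11.5).** Separate ineligibility at entry from the other reasons for withdrawal. Make the main analysis participants who met 6.1 and 6.2 and have the paired tests needed. Judge ineligibility from information that does not depend on the MAPLe result. Report the number excluded, with reasons, and repeat the analysis with all tested participants as a sensitivity check. Leave the handling of other withdrawals as now written.

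**Eligibility verification.** Reconcile 6.2, 8.1, 8.2 and Appendix 1 on how and when the perianal exclusions are verified. In particular, 8.1 places its checks after consent, 8.2 confirms eligibility at booking, and the examination row has no visit marked in the text supplied. How verification is done is a clinical matter for the investigators.

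**Cost.** A few sentences of text. A few participants may leave the main analysis: at an assumed 5%, 6 of 120, leaving 114, or 28.5 per group on average. Because section 8.3 has the student researcher undertake the assessment session, the plan must also say who judges late-found ineligibility and on what recorded information, so that the MAPLe result plays no part.
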